12.1 Regulatory and Ethical Considerations

The study will be conducted in accordance with Good Clinical Practice (GCP), 21 CFR Parts 50 and 56 and all applicable regulatory requirements.

Pre-menopausal women, post-menopausal women, and men are known to have major differences in their metabolism of omega-6 and omega-3 fatty acids (44-48). Specifically, pre-menopausal women efficiently convert dietary omega-6 and omega-3 18-carbon precursors (omega-6 LA and omega-3 alpha-linoleic acid) into omega-6 AA and omega-3 DHA, which compete for incorporation into tissue membranes (44, 46, 49, 50). Critically omega-6 AA is the immediate metabolic precursor to endocannabinoids (13), the primary outcome of the study. This efficient conversion is due to the effects of estrogen on liver enzymes (46, 49). Because endocannabinoids regulate hunger, satiety and metabolism, we expect pre-menopausal women to uniquely benefit from lowering dietary LA. By contrast, men and post-menopausal women are inefficient converters of omega-6 and omega-3 18-carbon precursors to AA and DHA (14, 44, 46). Because low LA diets are not expected to efficiently reduce tissue concentrations of AA, or its endocannabinoid derivatives in post-menopausal women and men, they are considerably less likely to benefit from lowering dietary LA.

12.2 Equitable Inclusion

The study population will consist of non-pregnant, non-lactating female subjects. Subjects that fulfill the study criteria will be included regardless of race, ethnicity, socioeconomic, religious, political or similar factors. Based on open recruitment from the NIH federal employee population, the expected racial composition of the study population will be 20.3% African-American, 2.8% Hispanic, 15.9% Asian or Pacific Islander, 0.6% Native American and 60.4% White (based on Office of Personnel Management Demographic Statistics available at: <https://www.opm.gov/policy-data-oversight/data-analysis-documentation/federal-employment-reports/demographics/2010/table1mw.pdf>).

Only English speaking volunteers will be included in this study because several of the psychometric instruments (e.g. POMS, PANAS, FS, CPRS) have not been validated in other languages.

CNS IRB Protocol Template (rev.1-17-08)

12.3 Inclusion of children or other vulnerable subjects

No children will participate in this protocol because children metabolize fatty acids differently than adults, and weight gain is not necessarily undesirable in this growing population.

12.4 Justification of sensitive procedures

The controlled dietary variables to be modified in this study are linoleic acid and oleic acid, which are common nutrients in foods. There is minimal risk associated with adverse events as fatty acids in edible form are GRAS (generally recognized as safe) by federal regulatory agencies.

Procedures that may cause some discomfort to subjects:

- 1) Blood sampling: Trained medical personnel will carry out the blood draws which may cause some discomfort to the subject.
- 2) DEXA scan: Trained medical personnel will perform the scan to reduce discomfort and risk to the subject. The expected exposure for a scan is (0.001 rem) or less than one day's exposure to natural background radiation.
- 3) Psychiatric and Neuropsychological Assessment measures: Research team personnel trained in the administration of psychometric measures will assist the subject in answering survey questions in the vicinity of trained medical personnel. Any confusion or unexpected response will be taken into consideration for follow-up by the trained medical personnel.
- 4) Tissue Biopsy: Muscle and adipose tissue biopsies will be performed by trained medical personnel. Subject will be monitored for signs of undue discomfort. Medication and appropriate palliative care will be provided if necessary.
- 5) 3T MRI Scan: Trained personnel will perform the scan to reduce discomfort and risk to the subject. In the 3T scanner, it is possible that the patient may experience peripheral nerve stimulation resulting in a sensation of mild twitching, warmth or vibration. Medical staff will monitor the subjects and administer appropriate care if necessary.
- 6) Storage of Private Health Information in a Research Database: Clinical information from each subject will be stored in a retrievable database at NIH. This information will remain confidential and protected like the medical record of the subject. Information with identifiers will not be released to any investigators or agencies/companies without the explicit consent of the subject.
- 7) Storage of Patient Samples: Coded blood and tissue samples without patient names or personal identifiers will be stored in secured freezers at [name] or in the NIAAA Clinical Core lab freezers in the 1-SE area of the clinical center. Samples will be processed upon completion of the study and destroyed when analysis is complete.

Reasons for Sensitive Procedures:

- 1) Blood sampling: Procedure is necessary to find the tissue fatty acids concentrations and [eCBs]. Previous work in this area has been performed successfully in rodents, but has not been translated to humans in a clinical trial.
- 2) DEXA Scan: Accurate determination of body composition is essential for determining the contribution of dietary fatty acids on body composition.
- 3) Psychiatric and Neuropsychological Assessment measures: These assessments are critical for determining each subject's eating habits, mood, and propensity for addictive behavior at each stage in the dietary intervention.
- 4) Tissue Biopsy: Muscle and adipose tissue biopsies are needed to determine local and specific tissue compositional changes due to the changed LA composition of the diets.

- 5) 3T MRI Scan: Non-invasive imaging for body composition is necessary to avoid the risks of deep tissue sampling of subjects for visceral fat and liver composition information.
- 6) Storage of Private Health Information in a Research Database: The storage of clinical information in retrievable databases is necessary to facilitate collaborative input and analysis. This information will remain confidential and protected like the medical record of the subject.
- 7) Storage of Patient Samples: The storage of clinical samples is necessary for collaboration and assurance of similar analysis conditions across all of the study samples.

Notes on Secure Data and Sample Storage:

Data will be collected and entered on form sets labeled with a unique coded identifier that is not related to the patient's name or any other personal identifier (Soc Security number, NIH employee number, etc).

Data will be kept in a locked cabinet or in secure computer files with access only for the Principal Investigator (PI) and Associate Investigators (AIs) involved with the study. When entered into the electronic databases, information will be under the CRC and NIH network regular access control. In addition, any information allowing the identification of the participants will be removed. The only possibility to reconstruct the link between database records and information will be through the unique identifier. The translation key will be stored in a locked cabinet or secure computer file with access available only to the PI and AIs named in this protocol document.

Blood and tissue samples will be destroyed after all of the analyses are completed. Research data will be stored for seven years following the study and destroyed according to NIH guidelines.

12.5 Safeguards for vulnerable populations

No vulnerable populations are recruited into this study. Although NIH employees may participate, study investigators and their superiors, subordinates and immediate family members (adult children, spouses, parents, siblings) will be excluded. Non-pregnant, non-lactating females will be recruited; but pregnancy testing will be provided for these females before sensitive procedures if deemed reasonable and/or necessary.

16.1 Data Safety and Monitoring Board

The main dietary intervention protocol uses standard clinical and laboratory procedures to study the effects of modifying dietary LA on body composition and response. Since the research procedures are to be performed in adult subjects and such procedures involve minor increase over minimal risk, the collection, monitoring and analysis of adverse events will be the responsibility of the Principal Investigator and the investigative team. No DSMB will be convened.

16.2 Data Safety and Monitoring Plan

Elements of the Data Safety and Monitoring Plan

- (1) Monitoring mechanism:

The Principal Investigator and the investigative team will monitor the protocol participant daily meal visit data for signs of participant distress and signs of dietary non-compliance.

(2) Frequency:

The Principal Investigator will meet with study staff weekly to discuss participant well-being and study progress.

(3) Stop or change rules:

The study will be stopped when 64 participants finish the diet phase. In the unlikely situation that multiple participants experience adverse events resulting from the consumption of the study foods, these events will be reported to the IRB and the study will be evaluated for continuation if these events are determined to be serious and life-threatening. Participants will be removed from the diet at the recommendation of the nutrition team or if they display signs of a serious adverse event or non-compliance as evaluated by the Principal Investigator, Lead Associate Investigator(s) or nutrition or medical staff.

(4) Advanced Plans:

No interim or futility analyses are planned. The study requires more cohort to reach the estimated sample size of 64 participants.

(5) Information to be monitored:

- a. Attendance at daily meal visits as recorded in participant medical record;
- b. Daily vital signs as recorded in participant medical record;
- c. CPRS to monitor participant mood as stated on page 26.

(6) Communication:

A record of participants removed from the diet phase will be reported to the Addictions IRB at the time of annual review. Serious adverse events will be reported according to the required NIH Clinical Center guidelines as stated in section 17 on the next page.

16.3 Data Monitoring for Quality Assurance

Data monitoring for quality assurance will be the responsibility of the Principal Investigator and the investigative team.

(1) Monitoring mechanism:

The Principal Investigator and the investigative team will monitor the protocol participant questionnaire data and participant binder data.

(2) Frequency:

As stated above, paper questionnaire data and other information in the participant binders will be reviewed bimonthly.

(3) Information to be monitored:

PANAS, POMS and FS psychometric data for each participant will be evaluated for self-report form completeness and status of data entry. Location and status of participant biospecimens will also be tracked and recorded in study sample spreadsheet logs. Status of imaging data will also be noted.

(4) Communication:

Missing psychometric data will be reported to the Principal Investigator and summarized in a report to the IRB at the time of annual review. A summary record of participants who refuse participation in the biopsies and MRI scan will also be reported to the IRB at the time of annual review.

17. Adverse Event Reporting

Adverse events

In the course of a dietary study, adverse events may occur. Unanticipated adverse events that occur as a direct result of research studies initiated at the NIH, but not related to the natural history of the underlying disease will be summarized at the time of the annual review.

Serious Adverse events

A serious adverse event is any adverse experience that:

1. Results in death;
2. Is life threatening;
3. Results in hospitalization or prolongs hospitalization;
4. Results in persistent or significant disability/incapacity;
5. Results in congenital anomaly/birth defect; or
6. Results in a condition, which in the judgment of the investigator represents a significant hazard.

Serious adverse events that are possibly, probably or definitely related to participation in research studies performed at the NIH Clinical Center will be reported. However, serious adverse events (other than death) that are clearly and unambiguously due to extraneous causes (accidental, environmental or coincidental events) will not be reported.

All serious adverse events will be reported using the NIH Serious Adverse Event Report Form to the NIAAA CNS IRB, and NIAAA Clinical Director as soon as possible, but no later than seven days of death or life threatening serious adverse event or within fifteen days after the occurrence of all other forms of serious adverse events.

18. Alternatives to participation or alternative therapies

Subjects are healthy volunteers and are not recruited for the treatment of a medical condition. Participants are counseled to continue their usual medical care for the duration of the study.

19. Confidentiality

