The biopsy tissue specimens will be separated into two aliquots for muscle and three aliquots for adipose tissue for assessment of fatty acid composition and other biochemical assays, frozen in dry ice and stored at -80°C for future studies.

Post-biopsy pain will be evaluated using the standard Clinical Center Numeric Rating Scale (Score range 0-10) before and after the biopsy, and twice daily (upon awakening and at lunch time) for 3 additional days.

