A subset of participants will also receive 1 to 2 grams of omega-3 EPA and DHA from fatty fish. There is a theoretical increase in bleeding times with omega-3 fatty acid intake. However, human supplement trials, including trials with considerably higher doses of omega-3 fatty acids, have not found increased bleeding risk (40, 41), with or without concurrent use of antithrombotic medications. We will use doses from foods that well within the usual daily intakes of populations with regular fish intake, such as Japan

and Iceland (42, 43). Therefore, there is little concern for increased risk due to increased omega-3 fatty acid intake.

It is possible that participants could have an allergic response to study foods. During the screening visit, participants will provide information on known dietary allergens and the diets will be adapted accordingly, or if necessary the participants will be excluded. Participants will also be advised to alert the research staff as soon as possible if they experience symptoms such as rash, hives, wheezing, or other signs of food allergy.

With any change in dietary intake there is potential for gastrointestinal distress in human subjects. Subjects will be asked to report signs of distress. Participants will be advised to use appropriate medications and/or digestive aids (H2 blockers, bean-o, etc) as necessary.

This study also requires daily workday visits to NIH for 12 weeks. It requires that participants only eat the food we provide. They may find these requirements inconvenient or burdensome. They may not like the study foods. Each of the study diets is nutritionally complete so it is unlikely that eating the diet will compromise health.

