8.4 Muscle and adipose tissue biopsies and tissue procurement

The major risks/discomforts include pain, bruising, infection, and scarring. The procedures will be performed under sterile technique to minimize the chances of infection. Local anesthetic will be used to minimize pain. Ice will be applied to the site immediately after the procedure to limit bruising, swelling and tenderness. After subcutaneous tissue biopsy, patients will be monitored by a nurse. Post-biopsy the incision site will be cleaned and closed with adhesive wound closures and covered with gauze and translucent dressing tape. Study participants will be instructed to report to the clinical staff any changes at

the biopsy site including bleeding, secretion, erythema, pain, and signs and symptoms of infection. Study participants will be instructed to self-monitor the incision site after discharge from the Clinical Center.

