In the course of a dietary study and infusion amendment, adverse events may occur. Unanticipated adverse events that occur as a direct result of research studies initiated at the NIH, but not related to the natural history of the underlying disease will be summarized at the time of the annual review.

Serious Adverse events

A serious adverse event is any adverse experience that:

1. Results in death;
2. Is life threatening;
3. Results in hospitalization or prolongs hospitalization;
4. Results in persistent or significant disability/incapacity;
5. Results in congenital anomaly/birth defect; or

6. Results in a condition, which in the judgment of the investigator represents a significant hazard.

Serious adverse events that are possibly, probably or definitely related to participation in research studies performed at the NIH Clinical Center will be reported. However, serious adverse events (other than death) that are clearly and unambiguously due to extraneous causes (accidental, environmental or coincidental events) will not be reported.

All serious adverse events will be reported using the NIH Serious Adverse Event Report Form to the NIAAA CNS IRB, and NIAAA Clinical Director as soon as possible, but no later than seven days of death or life threatening serious adverse event or within fifteen days after the occurrence of all other forms of serious adverse events.

S17. Alternatives to participation or alternative therapies

Subjects are healthy volunteers and are not recruited for the treatment of a medical condition. Participants are counseled to continue their usual medical care for the duration of the study.

S18. Confidentiality

Medical records

This information will remain confidential and protected according to NIH guidelines. Some clinically relevant research data will be stored indefinitely in the medical record and will be accessible to the patient for review by others of their choosing (doctors, insurance companies etc.) after executing a release of information.

Research Data

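### The routine summary of non-serious adverse events leaves out harms the protocol itself predicts, and no adverse-event grading scale or table by diet is planned

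*Combined protocol and SAP*

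**What the plan says.** The general rule in Section 17 for events that are not serious puts only these into the annual review: "Unanticipated adverse events that occur as a direct result of research studies initiated at the NIH, but not related to the natural history". S16 opens with "In the course of a dietary study and infusion amendment, adverse events may occur" and repeats the rule: "Unanticipated adverse events that occur as a direct result of research studies initiated at the NIH". Related serious events have their own rule in both sections, and it does not depend on whether the event was expected.

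The protocol names harms in advance. Section 8.2: "It is possible that participants could have an allergic response to study foods", and "With any change in dietary intake there is potential for gastrointestinal distress in human subjects". Section 8.3 names discomfort, bruising and, rarely, fainting or infection from blood draws. Section 8.4, on biopsies: "The major risks/discomforts include pain, bruising, infection, and scarring". S7 lists discomfort and bruising at the intravenous site, allergy, infection and burns for the infusion.

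Some information on these harms is gathered. Section 8.2 asks women to report gastrointestinal distress and allergy symptoms. Section 8.4: "Study participants will be instructed to report to the clinical staff any changes at" the biopsy site. Section 7.6.3: "Post-biopsy pain will be evaluated using the standard Clinical Center Numeric Rating Scale (Score range 0-10) before and after the biopsy", then twice daily for three further days.

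Section 16.1 gives the investigators responsibility for collecting, monitoring and analysing adverse events, and convenes no DSMB.

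**The concern.** The filter selects events by expectedness and attribution before anything is counted. In a feeding study with repeated biopsies and an intravenous tracer, the most likely non-serious harms are those already foreseen, and these are what the routine summary excludes. Attribution as an entry condition adds a judgement to each case. A mild complaint thought unrelated drops out before its frequency can be compared across diets.

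The design gives a planned table more weight. Under Section 7.6.2 only the research dietitian knows the allocation, and no DSMB sees data by arm. The weekly staff review in Section 16.2(2) is not set up to notice complaints clustering on one diet. S3 also says the infusion methods piloted here can be adapted to study other variables, so the frequency of complications per infusion would be useful to later investigators.

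**Working it through.** The plan states no safety figure, so there is none to reproduce. The check sets the reporting rule beside the predicted harms, the collection of data and the analysis plan.

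**1. Does each predicted harm, when not serious, meet the annual-summary rule?**

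| Harm | Named in | How it reaches the team | Inside the rule? | Another route |
|---|---|---|---|---|
| Gastrointestinal distress | 8.2 | Participant report | No, foreseen | 16.2(3) if several women and food-related |
| Food allergy | 8.2 | Participant report | No, foreseen | 16.2(3), same condition |
| Blood-draw bruising, fainting | 8.3 | Staff present at the draw | No, foreseen | None stated |
| Biopsy bruising, infection, scarring | 8.4 | Participant report | No, foreseen | None stated |
| Biopsy pain | 8.4, 7.6.3 | 0-10 scale, scheduled | No, foreseen | None stated |
| Infusion-site discomfort, bruising | S7 | Staff present | No, foreseen | None, unless she is removed from the substudy |

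**2. Does another section supply the summary?**

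- Section 10 lists no adverse-event outcome. Section 11 has no safety analysis, and its exploratory aims are tied to the outcomes in Section 10. Affective states are a secondary outcome, so mood would be analysed. Biopsy pain scores appear in neither section.
- The headings of Section 9 and S8 mention grading, but neither section gives a scale.
- Section 16.2(5) monitors attendance, vital signs and a mood scale. S15.2(5) monitors vital signs only.
- The annual reports in 16.2(6), 16.3(4), S15.2(6) and S15.3(4) cover removals, serious events, missing psychometric data, refusals of biopsy or MRI, substudy recruitment and enrolment, and infusion adjustments. None lists expected non-serious events.

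**3. How far does Section 16.2(3) reach?** It sends food-related events in more than one participant to the IRB, with no condition that they be unanticipated. It ends with a condition that the events be serious and life-threatening. If that condition governs only the decision on continuing the study, clusters of mild food-related events are reported. If it governs the reporting too, they are not. The sentence allows both readings. On either, it excludes single cases and biopsy or infusion harms, and asks for no comparison by diet.

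**4. Scope.** Section 7.4 randomises 84 women and expects 64 to complete.

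- Ceiling on main-study biopsy sessions (baseline and day 84): 84 × 2 = 168.
- At the expected completion: 84 + 64 = 148.
- The 84 baseline sessions precede randomisation and cannot show a diet effect. About 148 − 84 = 64 can.
- Refusals (16.3) and muscle biopsies not attempted (7.6.3) lower these counts.
- Infusions: at most 12 × 2 = 24 (S6).

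**The case against.** The best counter-argument is that Section 17 governs annual reporting to the IRB. It says nothing about the final analysis or publication, and Section 16.1 assigns adverse-event analysis to the investigators. Section 16.2(3) gives food-related clusters their own route, removals are reported each year, mood is an outcome and biopsy pain is scored. In a mechanistic feeding study of healthy volunteers, the omission could be called a matter of completeness.

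Much of this stands. A reader might infer that predicted harms would never be reported, or that an excess on one diet could not be seen. The documents support neither. Section 16.2(3) can bring expected food-related events to the IRB, and nothing forbids a final table by diet.

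It is also fair that the documents do not define *unanticipated*. Treating a harm named in the risk section as anticipated is the natural reading, but it is firmer for biopsy pain or gastrointestinal distress than for events described as rare or unlikely, such as fainting or an infusion burn. Bleeding on the omega-3 diet should not be counted, because Section 8.2 calls the effect theoretical and of little concern.

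The objection does not supply a method. Section 16.1 names no population, grading or table, and 16.2(3) does not cover procedures.

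**Conclusion.** The point holds in this form: the routine annual summary excludes non-serious harms the protocol foresees, and the plan specifies no grading scale and no adverse-event summary by randomised diet or by procedure. Related serious events are outside the criticism.

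Its size is a matter of scope. It affects the safety information on 84 women, about 148 main-study biopsy sessions (168 at most) and up to 24 infusions. No rate of missed events can be given, because the documents state no expected rate for any harm. The conclusion assumes that a harm listed in the risk sections counts as anticipated, and that the rule is applied as worded. Nothing is inferred from sections removed before review. The primary comparison is unaffected, but the correction is worth making because it is cheap and the omission is selective.

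**What to change.** In Sections 17 and S16, replace the filter with a statement that all reported adverse events will be listed and summarised, whatever their expectedness or attribution. Keep both as columns. Name a grading scale in Sections 9.1 and S8. Reword 16.2(3) so that it is clear what its closing condition qualifies.

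In Section 11, add descriptive tables:

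- number and proportion of women with each event, by randomised diet, among all randomised women, for the 12-week diet phase;
- the continuation phase described separately, without comparison, since only diet B continues;
- biopsy complications and pain score (peak, and change from before the biopsy) per procedure performed, with baseline biopsies shown apart because they precede randomisation;
- infusion events per infusion.

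These change recording and reporting only and leave clinical care as it is. The cost is wording in a few sections, a small set of tables, a simple event log and some data entry. The log is needed because, apart from the scheduled pain scores, the documents describe no form or schedule for these harms. Section 16.2(4) reads as if recruitment is under way, so the tables should say from what date events were logged in this way.
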